1.2 Background

Prostate cancer is the most commonly diagnosed cancer and second leading cause of cancer death in American men (1). Existing conventional imaging (CT, MRI and bone scans) has a low sensitivity in detecting local recurrence or metastatic disease (2). The one exception being NaF PET/CT for the detection of osseous metastasis. Due to this limitation, numerous approaches to stage patients have been evaluated.

Choline imaging has been frequently used, as prostate cancer exhibits increase choline uptake that has been associated with the presence of choline kinase (3). Choline uptake is increased in comparison to FDG in both androgen dependent and independent prostate cancer patients (4). Choline has also been shown to be sensitive for the detection of recurrent tumor in patients with PSA (prostate specific antigen) values of less than 1.0 ng/ml (5). There are two forms of choline that are used in imaging prostate cancer, C-11 and F-18 choline. C-11 choline has a short half-life of 20 minutes, which limits its detection for metastatic disease but results in improved local detection due to decreased urinary activity at the time of imaging. F-18 choline has significant urinary excretion that limits evaluation of the prostate but, but has been shown to have better detection rates for distant metastatic disease (6). C-11 choline has limited sensitivity for osseous metastasis, possibly due to the decreased uptake time (7). Additionally, the sensitivity of C-11 choline is limited in patients with PSA values < 1.0 ng/ml (8-10). Although choline PET may be limited in sensitivity, it clearly delineates more lesions than cross section imaging or bone scan in patients with known disease (11). In 2012, the Mayo Clinic obtained NDA (new drug application) approval from the FDA for the use of C-11 choline.

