2.2 Secondary

- Sensitivity and PPV on a per-patient and per-region-basis (Table 1) of ⁶⁸Ga-PSMA-11 PET for detection of tumor location confirmed by histopathology/biopsy *and* conventional imaging follow-up.

- Sensitivity, specificity, and negative predictive value (NPV) on a per-patient basis of ^{68}Ga -PSMA-11 PET for detection of tumor location confirmed by histopathology/biopsy and conventional imaging follow-up.
- Detection rates on a per-patient basis of ^{68}Ga -PSMA-11 PET stratified by PSA value (0.2 - <0.5, 0.5 - <1.0, 1.0 - <2.0, 2.0 - <5.0, 5.0).
- Impact of ^{68}Ga -PSMA-11 PET on clinical management in BCR patients.
- Inter-reader reproducibility
- Safety.

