3.3.1 Inclusion Criteria

1. Histopathological proven prostate adenocarcinoma.
2. Rising PSA after definitive therapy with prostatectomy or radiation therapy (external beam or brachytherapy).

- a. Post radical prostatectomy (RP) – AUA recommendation
 - i. PSA greater than 0.2 ng/mL measured more than 6 weeks after RP and,
 - ii. Confirmatory persistent PSA greater than 0.2 ng/mL
- b. Post-radiation therapy –ASTRO-Phoenix consensus definition
 - i. Nadir + greater than or equal to 2 ng/mL rise in PSA
3. Karnofsky performance status of ≥ 50 (or ECOG/WHO equivalent).
4. Age > 18.
5. Ability to understand a written informed consent document, and the willingness to sign it.

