6.1.1.1 Screening Assessments

The Screening procedures and assessments must be completed within 30 days of the day 1 Visit.

- Laboratory values: all patients must have a recent PSA (within 30 days prior to study enrollment) consistent with BCR

- Pathology: all patients must have histopathology/biopsy of the prostate with a documented Gleason score
- Performance status: all patients must have their Karnofsky performance status (or ECOG/WHO equivalent) evaluated (Appendix A).

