^{68}Ga -PSMA-11 PET positive findings will be validated as true or false positive as outlined in more detail below. False negative ^{68}Ga -PSMA-11 PET findings cannot be determined as this would require biopsies of ^{68}Ga -PSMA-11 negative but conventional or functional non- ^{68}Ga -PSMA-11 PET positive imaging lesions. Inclusion of such patients however would be violation of the inclusion criteria.

^{68}Ga -PSMA-11 PET validation based on follow-up imaging:

- i) Lymph nodes will be assessed by change in size. ^{68}Ga -PSMA-11 positive lymph nodes will be considered:
 - (1) True positive:
 - If on follow-up imaging within 3-12 months, lymph nodes seen on CT or MRI decrease by more than 30% (for patients undergoing systemic treatment of focal therapy at this site) or increase by more than 20% in short axis diameter (with a minimum of 3 mm in change in size).
 - If patients with solitary lymph node regions show a decrease of PSA by greater than 50% after targeted treatment (i.e. external beam radiation) and the lymph nodes do not change in size (less than 30% decrease or less than 20% increase in short axis diameter).
 - (2) False positive:

- If on follow-up imaging within 3-12 months, sites of initial⁶⁸Ga-PSMA-11 positive lymph node lesions seen on CT or MRI decrease by more than 30% *without* systemic therapy or focal therapy at this site.
 - If ⁶⁸Ga-PSMA-11 positive lymph node lesions do not meet the criteria for above false positive or true positive findings.
- ii) Visceral lesions (non-lymph node soft tissue or organ) will be assessed by change in size. ⁶⁸Ga-PSMA-11 positive visceral lesions will be considered:
- (1) True positive:
- If on follow-up imaging within 3-12 months, visceral lesions seen on CT or MRI decrease by 30% (for patients undergoing systemic treatment of focal therapy at this site) or increase by 20% in largest diameter.
 - If patients with solitary visceral metastasis show a decrease of PSA by greater than 50% after targeted treatment (i.e. external beam radiation) and lesions do not change in size (less than 30% decrease or 20% increase in largest diameter).
- (2) False positive:
- If on follow-up imaging within 3-12 months, sites of initial⁶⁸Ga-PSMA-11 positive lymph node lesions seen on CT or MRI decrease by more than 30% *without* systemic therapy or focal therapy at this site.
 - If ⁶⁸Ga-PSMA-11 positive lymph node lesions do not meet the criteria for above false positive or true positive findings.

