8.3.3 Analysis of Secondary Endpoints

PPVs on a per-patient and per-region-basis of ^{68}Ga -PSMA-11 PET for detection of tumor location confirmed by histopathology/biopsy and conventional imaging follow-up will be calculated and reported along with the corresponding two-sided 95% confidence intervals. The paired McNemar's test will be used to compare the PPVs of ^{68}Ga -PSMA-11 PET imaging to the PPVs of conventional imaging.

Sensitivity, specificity, and NPVs on a per-patient basis of ^{68}Ga -PSMA-11 PET for detection of tumor location confirmed by histopathology/biopsy will be summarized in tabular format. Furthermore, the positive and negative likelihood ratios (LR+ and LR-) will be calculated and reported. Ninety-five confidence intervals of sensitivity, specificity, and NPV will be calculated using the Wilson score method. The comparisons of sensitivity, specificity, and NPV on a per-patient basis of ^{68}Ga -PSMA-11 PET imaging will be compared to of sensitivity, specificity, and NPV on a per-patient basis of conventional imaging using a paired McNemar's test.

Detection rates on a per-patient basis of ^{68}Ga -PSMA-11 PET stratified by PSA value (0.2 - <0.5, 0.5 - <1.0, 1.0 - <2.0, 2.0 - <5.0, 5.0) will be summarized in tabular format and compared between PSA strata using chi-square analysis. The impact of ^{68}Ga -PSMA-11 PET on clinical management in BCR patients will be evaluated using descriptive statistics.

9 Study Management

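### Per-patient specificity, NPV and likelihood ratios are planned in an all-recurrence cohort that has no credible negative reference

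*Combined protocol and SAP*

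**What the plan says.** Section 2.2 lists "Sensitivity, specificity, and negative predictive value (NPV) on a per-patient basis" as a secondary objective, and 2.3.2 repeats it as an endpoint. Its reference standard is the same as for the objective before it: "for detection of tumor location confirmed by histopathology/biopsy *and* conventional imaging follow-up". Section 8.3.3 analyses the same measures but words the reference differently. There the per-patient figures "for detection of tumor location confirmed by histopathology/biopsy will be summarized in tabular format", with no mention of conventional imaging. It then says that "the positive and negative likelihood ratios (LR+ and LR-) will be calculated and reported" and plans paired McNemar tests of PET against conventional imaging for sensitivity, specificity and NPV.

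On the population, 6.1.1.1 says that "all patients must have a recent PSA (within 30 days prior to study enrollment) consistent with BCR", in line with 3.3.1. No group without recurrence is enrolled.

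On negative findings, 8.3.2 says that false-negative PET findings "cannot be determined as this would require biopsies of" lesions that are negative on PSMA PET but positive on other imaging. Its rules, by follow-up imaging and by biopsy, sort PET-positive findings into true and false positives. No rule defines a true negative.

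On the follow-up modalities, 1.2 says: "Existing conventional imaging (CT, MRI and bone scans) has a low sensitivity in detecting local recurrence or metastatic disease".

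**The concern.** Specificity, NPV and both likelihood ratios need patients who can credibly be called negative by a standard better than the test under study. Here every patient enters because PSA shows recurrence, and the plan itself says that missed disease cannot be identified. The only standard on offer for PET-negative patients is imaging that the plan describes as insensitive.

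At stake is how these results would be used. Section 1.1 says the data are to be pooled for a new drug application. An NPV that is high because follow-up imaging seldom finds anything could be taken as evidence that a negative PET rules out locatable disease. The comparison with conventional imaging would inherit the defect.

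**Working it through.** **The plan's own figures.** The plan gives no expected value, sample size or precision for specificity, NPV or likelihood ratios. Its only sizing is for PPV, 50% against 70% at one-sided 0.01 with 90% power. The normal approximation gives ((2.326 × 0.5 + 1.282 × √0.21) / 0.20)² = 76.6, so 77 against the stated 75. Nothing below depends on this.

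**Inputs.**
- N = 1,500 patients (3.2, 8.2.1).
- PET detection rate d: 50% at PSA below 1 ng/ml, above 85% at PSA over 2 ng/ml (1.2). No overall rate or PSA mix is given.
- PPV = 70% (the hypothesis in 8.2.1).
- Biopsied: about 25%, that is 0.25 × 1,500 = 375 (8.2.1), aimed at PET-positive findings (8.3.2, part c).
- c = share of PET-negative patients in whom follow-up finds disease. The documents do not give it. Assumed range: 5% to 60%.

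**Step 1: what each measure needs.** Specificity = TN/(TN + FP). NPV = TN/(TN + FN). LR+ = sensitivity/(1 − specificity) and LR− = (1 − sensitivity)/specificity, with sensitivity = TP/(TP + FN). Section 8.3.2 says FN cannot be determined and gives no rule for TN. On that statement NPV and LR− cannot be computed. Specificity lacks its TN, and LR+ lacks both.

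**Step 2: PET-negative patients.** 1,500 × (1 − 0.85) = 225 and 1,500 × (1 − 0.50) = 750, so roughly 225 to 750.

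**Step 3: combined reference (2.2).** Suppose that, despite 8.3.2, positive follow-up imaging is counted as FN and unremarkable follow-up as TN. Then FN = N(1 − d)c and TN = N(1 − d)(1 − c), so

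NPV = TN/(TN + FN) = 1 − c.

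This gives 90% at c = 10% and 60% at c = 40%, whatever the detection rate. At those shares, between 225 × 0.60 = 135 and 750 × 0.90 = 675 patients with biochemical recurrence would be tabulated as true negatives.

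With TP = N × d × 0.70 and FP = N × d × 0.30:

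| d | c | TP | FP | FN | TN | NPV | Specificity | LR+ | LR− |
|---|---|---|---|---|---|---|---|---|---|
| 50% | 5% | 525 | 225 | 38 | 712 | 95% | 76% | 3.9 | 0.09 |
| 50% | 60% | 525 | 225 | 450 | 300 | 40% | 57% | 1.3 | 0.81 |
| 85% | 5% | 892 | 383 | 11 | 214 | 95% | 36% | 1.5 | 0.03 |
| 85% | 60% | 892 | 383 | 135 | 90 | 40% | 19% | 1.1 | 0.69 |

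The less the follow-up imaging finds in PET-negative patients, the better PET looks on every measure. For NPV this is exact. For the other three it holds with PPV fixed at 70%.

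The McNemar comparison is circular under this reference, because conventional imaging helps to define the truth against which it is compared.

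**Step 4: biopsy-only reference (8.3.3).** About 375 patients are biopsied, and the biopsies are aimed at PET-positive findings. The 225 to 750 PET-negative patients would contribute almost nothing to TN or FN. The problem is then selective verification, not insensitive follow-up imaging.

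**The case against.** The strongest reply concerns the target. The measures are defined for confirmed tumor location, not for whether the patient has cancer. Biochemical recurrence is a PSA definition, and no section says that every enrolled patient has disease that can be located. A patient with no confirmed location is a legitimate reference negative for that target. This stands, and it limits the point.

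A reader might go further and infer that, since all patients have recurrence, true NPV is about zero and specificity has no denominator. The documents do not support that reading. It answers a different question from the one the plan asks. The plan's own rules also produce reference negatives: FP + TN in the table runs from 383 + 90 = 473 to 225 + 712 = 937. The 100% row in the power table of 8.2.1 is no evidence for it either, since it is the sum of the regional shares (30 + 15 + 20 + 35).

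It would also be too strong to say that specificity and LR+ measure only what follow-up imaging misses. They depend on false positives as well, through negative biopsies and the default to false positive for unconfirmed lesions. At d = 50% and c = 5%, specificity is 66%, 76% or 91% when PPV is 50%, 70% or 90%. At d = 85% and PPV 70% it is 19% to 36%, which reassures nobody.

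Finally, these are secondary, unpowered measures, and a stated limitation might seem enough. But a caveat does not supply a missing true-negative rule, settle which reference applies, or remove the conflict with 8.3.2.

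**Conclusion.** The point holds as a defect in the planned secondary analysis. Per-patient specificity, NPV, LR+ and LR−, and the comparisons of specificity and NPV with conventional imaging, have no credible negative reference under either wording of the standard. With the combined reference, NPV restates how little follow-up imaging finds. With biopsy alone, PET-negative patients are hardly observed. Section 8.3.2 says outright that one of the required cells cannot be filled.

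The size can only be shown as a range: NPV of 60% to 90% for assumed shares of 40% to 10%, applied to roughly 225 to 750 PET-negative patients. It assumes that the cited detection rates bracket this cohort and that every PET-negative patient has follow-up imaging. Section 8.3.2 promises that imaging, but the schedule in 6.1 does not list it and 3.4 ends follow-up after one day.

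The primary PPV analysis is not affected. Per-patient sensitivity, a primary objective in 2.1, is affected, because it too needs false negatives.

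**What to change.** - In 2.2, 2.3.2 and 8.3.3, and the matching line of the Abstract, delete per-patient specificity, NPV, LR+ and LR− wherever they appear, with the comparisons of specificity and NPV with conventional imaging. Report per-patient PPV and detection rate.
- If a negative-side measure is kept, call it agreement with follow-up imaging, not specificity or NPV. A per-region version has the advantage that patients with recurrence do have disease-free regions, but state that it shares the same low-sensitivity reference. It also needs the follow-up imaging to be available, so 8.3.2 must be reconciled with 3.4 and 6.1.
- Use one reference standard for these measures in 2.2 and 8.3.3.
- Reconcile the statement on false negatives in 8.3.2 with the planned per-patient sensitivity. Do not let sensitivity drop out silently. One option is to label it as relative to confirmed disease only.

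The cost is wording: some secondary figures are dropped or relabelled. Deletion needs no new data.

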3.2 Number of Subjects

It is anticipated that 125 patients per year over three years will be enrolled in this study, for a total of 375 at UCSF. In total we aim to enroll 1,500 patients across all sites.

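### The pooled chi-square across PSA strata mixes PSA level with entry route for contrasts across 2.0 ng/mL, because radiation-criterion entrants cannot fall in the three lowest strata

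*Combined protocol and SAP*

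**What the plan says.** Section 2.2 lists as a secondary objective "Detection rates on a per-patient basis of" the agent by PSA level. Section 8.3.3 gives the classes, "stratified by PSA value (0.2 - <0.5, 0.5 - <1.0, 1.0 - <2.0, 2.0 - <5.0, 5.0" (the last is read here as 5.0 and above), and says that the rates "will be summarized in tabular format and compared between PSA strata using chi-square analysis". No section splits, stratifies or adjusts this comparison by prior therapy.

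Section 3.3.1 has two routes of entry:

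- After prostatectomy: "PSA greater than 0.2 ng/mL measured more than 6 weeks after RP and" a confirmatory value above the same threshold.
- After radiation: "Nadir + greater than or equal to 2 ng/mL rise in PSA".

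Section 6.1.1.1 ties the entry value to the present: "all patients must have a recent PSA (within 30 days prior to study enrollment) consistent with BCR". On enrolment, section 3.2 states "In total we aim to enroll 1,500 patients across all sites", and "for a total of 375 at UCSF".

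**The concern.** The two entry criteria have different PSA floors, and the PSA classes straddle the higher one. When a stratum below 2.0 ng/mL is compared with one above it, PSA rises and the make-up of the group can change too, from prostatectomy-criterion entrants only to a mixture of both routes. If detection at a given PSA differs between routes, part of the difference between low and high strata reflects who was eligible rather than PSA.

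The plan names a test for this comparison, so it goes beyond description. Section 1.2 cites detection by PSA level as evidence for the agent, and section 1.1 says that the data are to be pooled for a marketing application. A significant result is likely to be read as a PSA effect. The strata are also ordered, and an unordered chi-square does not use that order.

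**Working it through.** **No figure to reproduce.** The plan gives no sample size, power or significance level for this comparison.

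**Step 1: which strata each route can reach.** On the radiation route, the lowest entry PSA is nadir + 2, and a nadir cannot be below 0.

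| Nadir (ng/mL) | Lowest entry PSA | Lowest stratum reached |
|---|---|---|
| 0 | 2.0 | 2.0 to <5.0 |
| 0.5 | 2.5 | 2.0 to <5.0 |
| 1 | 3.0 | 2.0 to <5.0 |
| 3 | 5.0 | 5.0 and above |

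The radiation route adds nobody to the three strata below 2.0. The prostatectomy route, with a floor of 0.2, can reach all five. This step needs only sections 3.3.1, 6.1.1.1 and 8.3.3.

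**Step 2: size of the shift.** Let f be the share of radiation-criterion entrants in the top two strata, and d the detection difference between routes at equal PSA.

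Pooled upper rate = (1 − f) × p + f × (p + d) = p + f × d, where p is the rate for prostatectomy-criterion entrants.

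The shift is f × d. The documents give neither f nor d. Assumed ranges are f = 25% to 75% and d = 5 to 20 points, either sign:

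- smallest: 0.25 × 5 = 1.25 points
- largest: 0.75 × 20 = 15 points
- if d = 0: no shift.

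**Step 3: effect on the test.** Illustration only. Assume no PSA effect within either route, 70% detection on the prostatectomy route, higher detection on the radiation route, 20% of patients per stratum, 4 degrees of freedom and a 5% level. For f = 50% and d = 10 points:

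- upper rate = 70 + 0.5 × 10 = 75%
- overall rate = 0.6 × 70 + 0.4 × 75 = 72%
- noncentrality per patient = (0.6 × 0.02² + 0.4 × 0.03²) / (0.72 × 0.28) = 0.0006 / 0.2016 = 0.00298
- noncentrality = 1.1 at 375 patients and 4.5 at 1,500.

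Probability that the pooled test rejects:

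| f | d (points) | N = 375 | N = 1,500 |
|---|---|---|---|
| 25% | 5 | 5.3% | 6.4% |
| 50% | 10 | 11% | 36% |
| 75% | 20 | 77% | >99% |

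With strata of 10, 10, 15, 30 and 35% of patients, the middle row becomes 11% and 35%. Section 8.3.1 can be read as leaving patients with histopathology out of the secondary analyses. That would give 1,500 − 375 = 1,125 patients, between the two sizes shown.

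**Step 4: what is lost by testing within the prostatectomy route.** Assume detection of 50, 50, 70, 85 and 85% across the strata (the end values follow the background figures in section 1.2; the middle one is assumed) and equal strata. Patients kept = N × [0.6 + 0.4 × (1 − f)].

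| f in the top two strata | Kept of 375 | Power | Kept of 1,500 | Power |
|---|---|---|---|---|
| 25% | 337 | >99% | 1,350 | >99% |
| 50% | 300 | >99% | 1,200 | >99% |
| 75% | 262 | 96% | 1,050 | >99% |

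These powers are for the unordered chi-square within that route; the trend test was not computed.

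**The case against.** The case for leaving the plan alone is substantial. This is one unpowered secondary comparison with no stated significance level or decision rule. The plan promises rates by PSA class and does not claim a PSA effect independent of prior therapy. The stratum rates remain valid descriptions of the patients enrolled. Section 1.2 cites 50% detection below 1 ng/mL and above 85% over 2 ng/mL, a gap of about 35 points. A shift of 1 to 15 points would neither create nor reverse such a gap. The rejection rates in Step 3 assume no PSA effect at all, which that background does not suggest, and the mildest case stays close to 5%. A chi-square on ordered groups is valid; it merely does not use the order.

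All of this stands, and it limits the weight of the point. It does not remove the structural fact that the test, as written, cannot separate PSA from entry route across 2.0 ng/mL.

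Three stronger readings are tempting, and the documents support none of them:

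- A reader might infer that the whole PSA gradient is confounded and applies to neither group. The three strata below 2.0 contain one route only, so their rates, and comparisons among them, apply directly to prostatectomy-criterion entrants.
- A reader might infer an upward bias of known size. With neither the route mix nor detection by route in the documents, the shift could have either sign or be zero.
- A reader might infer that a regression term for prior therapy settles the matter. The routes do not overlap below 2.0, so that term would rest on the top two strata and on the assumed form of the PSA effect.

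**Conclusion.** The point holds in a limited form. It is a worthwhile, inexpensive improvement to a secondary analysis. That the mixing is possible follows from the eligibility rules alone; its size, about 1 to 15 points, rests entirely on the assumed shares and differences.

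Two conditions apply. First, the claim concerns the criterion under which a patient qualified, not every patient who has ever had radiation. A man with prostatectomy and later salvage radiation might enter on the prostatectomy criterion and fall in a low stratum; the protocol does not say how he is classed. Second, section 8.3.3 does not say which PSA value sets the stratum. If it is not the qualifying value, a few radiation-criterion entrants could fall below 2.0, although the screening rule in section 6.1.1.1 limits this.

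**What to change.** In section 8.3.3:

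- Tabulate detection by PSA stratum separately by qualifying entry criterion (prostatectomy or radiation). State that a patient with prostatectomy and later salvage radiation is classed by the criterion under which he qualified, and state which PSA value sets the stratum.
- As the test of a PSA effect, replace the pooled chi-square with a trend test across the ordered strata, for example Cochran-Armitage, within prostatectomy-criterion entrants.
- Report the pooled stratum rates descriptively.
- If a logistic model on log PSA with an entry-route term is wanted, label it supportive only.

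PSA and the qualifying criterion are already needed for eligibility, so no new data are required. The cost is a little more analysis and a test on fewer patients. Under the assumptions in Step 4, that loss of patients has little effect on power.
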